9.3.4. Inpatient data capture

While the participant is in hospital, they will not be asked to complete the daily questions in the Patient Diary. If the participant is in hospital at days 7, 14, 21 or 30 post-operatively, they will be asked to complete the EQ-5D-5L assessment (days 7, 14, 21 and 30) and the SF-12 questionnaire (days 7 and 30). It is recommended that separate Quality of Life questionnaires (as used at baseline) be used whilst a participant is an inpatient but these forms in the Patient Diary can be used. If the participant is an inpatient at the time of the Day 30 assessment, the Bluebelle wound healing questionnaire does not need to be completed.

9.3.5. Outpatient data capture

Following discharge from the hospital, a Patient Diary will be used to record health care intervention, diagnosis of wound infection, dressing changes, antibiotics used and quality of life (EQ-5D-5L at day 7, 14, 21 and 30, and SF-12 at day 30). If the date of discharge is after day 7, then the relevant days that have passed whilst the participant is in hospital will be crossed off by the research team, ensuring that the participant starts to fill out the diary on the correct day. There will be no collection of health resource usage whilst the participant is in hospital.

To help with completing the diary, a member of the research team will contact the participant by telephone or text message (as dictated by participant choice) every week to provide assistance and also to arrange their outpatient review. Prior to the review at day 30, the Bluebelle wound healing questionnaire in the diary should be completed by the participant. If the day 30 review is completed in person the diary should be collected from the participant at this hospital visit. If the day 30 review is conducted remotely the participant should be reminded to post it back to the SUNRISE Trial Office.

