1. BACKGROUND AND RATIONALE

1.1. Background

Surgical site infection (SSI) is a preventable post-operative complication that causes significant pain, suffering and even death. SSIs affect at least 200,000 patients in the UK each year¹⁻³. At an average cost of £3500 per infection, SSIs currently cost the NHS approximately £700 million per year⁴. The rates and costs per patient are likely to be very similar in Australia, although there are no nationally collected statistics to reference. In addition to the financial burden of SSI, caused by prolonged post-operative inpatient stay and additional inpatient and outpatient treatment costs⁵⁻⁶, there is significant association between the development of an SSI and morbidity and mortality rates⁷. Patients who develop an SSI are twice as likely to die as those without SSI, and around one third of post-operative deaths are attributable, at least in part, to SSI⁸. With antibiotic resistance becoming an increasingly serious global issue, there is significant health need for high quality research in this area, to try to address this potentially avoidable complication and thereby benefit both patients and healthcare providers.

Negative pressure wound therapy (NPWT) has been used since the mid-1990s to manage and promote healing in chronic open wounds. The closed negative-pressure environment serves to prevent bacterial ingress and removes blood and serous fluid exuding from the wound. Single-use Negative Pressure Dressings (SUNPD) have been developed for use on primarily closed incisions. These devices are small, highly portable and simple to apply. Their use in studies of non-abdominal wall incisions has resulted in a 50-80% reduction in SSI⁹⁻¹⁰. However, no multicentre, randomised controlled trials exploring the clinical effectiveness of SUNPD in reducing SSIs in patients undergoing emergency abdominal surgery have been reported.

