9.2. Secondary Outcomes

- Length of hospital stay after surgery as measured from the date of index surgery to the date of discharge

- Wound complications within 30 days post-surgery as graded by Clavien-Dindo scale (see Appendix 2)
- Hospital re-admission for wound related complications within 30 days. These will include SSIs, wound breakdown/dehiscence, seromas and wound related pain
- Health-related Quality of Life assessed using the validated Short Form-12 (SF-12) questionnaire at baseline, and day 7 and day 30, and the EuroQuol-5 Dimension-5 Level (EQ-5D-5L) at baseline, day 7, day 14, day 21 and day 30. Pain at the site of the primary laparotomy will also be assessed, using a Likert scale of 1-10 at day 7 and day 30
- Serious adverse events up to 30 days
- Cost-effectiveness assessed using a patient diary for patient reported healthcare resource usage. Healthcare usage will be taken directly from the patient diaries and the costs attributable to this will be identified
- Patient acceptability of use of their dressing via an acceptability score using a Likert scale of 1-10 at day 7, reflecting participant's assessment of the acceptability of having the dressing
- In the UK only, Health professional's acceptability of use of SUNPD (via a survey of users). This will focus on the ease of application of the dressing, the care needed to maintain/monitor the dressing while it is in place and an overall assessment of health professional's experience of the dressing

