15. UK HEALTH ECONOMICS ANALYSIS

The health economic analysis will determine the costs and benefits of SUNPD versus the surgeon's preferred dressing. The economic evaluation will be conducted from the perspective of the NHS and personal social services.

Healthcare resource utilisation will be collected for each patient alongside the trial through a patient diary included as part of the CRF. Patients with an ongoing SSI at time of discharge will continue to complete the patient diary until healing of the SSI. Items of resource use will be costed using national sources and tariffs such as the Personal Social Services Research Unit and NHS reference cost databases.

Generic health-related quality of life data will be collected using the EQ-5D-5L instrument at baseline and each follow-up assessment. Base-case analyses will be conducted using the crosswalk value sets for the

EQ-5D-5L with sensitivity analyses conducted using the EQ-5D-5L value set for England. Quality adjusted life years (QALYs) will be calculated using the area under the curve approach, with regression-based adjustment for baseline EQ-5D-5L score and minimisation variables.

A trial-based economic evaluation will take the form of a cost-utility analysis with results presented as incremental cost-utility ratios (ICURs). Data will be analysed on an intention to treat basis. Sensitivity analysis will consider the impact of missing data using appropriate techniques. Deterministic and probabilistic sensitivity analysis will be undertaken to explore the robustness of the results to plausible variations in key assumptions and variations in the analytical methods used. Cost-effectiveness acceptability curves (CEACs) will be plotted to show the probability of the intervention being cost-effective considering a range of willingness to pay thresholds per additional QALY gained.

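### As written, the NHS-perspective economic evaluation draws resource use only from a diary that stops in hospital, so inpatient costs of SSI are given no route into the analysis

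*Protocol*

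**What the plan says.** Two sections set the source of resource use. Section 9.2, defining cost-effectiveness as a secondary outcome: "Healthcare usage will be taken directly from the patient diaries and the costs attributable to this will be identified". Section 15, on the UK economic analysis: "Healthcare resource utilisation will be collected for each patient alongside the trial through a patient diary included as part of the CRF". Neither names a second source.

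Two sections then switch that source off in hospital. Section 9.3.4: "While the participant is in hospital, they will not be asked to complete the daily questions in the Patient Diary". Section 9.3.5, for a discharge after day 7: "the relevant days that have passed whilst the participant is in hospital will be crossed off by the research team". The same section closes the paragraph with "There will be no collection of health resource usage whilst the participant is in hospital".

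Two statements pull the other way. Section 15: "The economic evaluation will be conducted from the perspective of the NHS and personal social services". Section 1.1 describes the financial burden of SSI as "caused by prolonged post-operative inpatient stay and additional inpatient and outpatient treatment costs".

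Outside the diary, the protocol records several inpatient items:
- post-operative length of stay and wound-related readmission within 30 days (9.2);
- a form for any return to theatre within 30 days (8.4);
- SUNPD changes (8.1) and the timing and reason of removal (8.3);
- the highest Clavien-Dindo grade of wound complication (9.3.6);
- drainage of wound infections, and prolonged stay or readmission for wound complications, on the routine wound assessment CRFs (10.3).

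The protocol does not say that these feed the economic evaluation, and it does not say that they are excluded.

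**The concern.** An NHS perspective includes hospital care. The protocol's own rationale puts part of the cost of SSI in hospital, and section 3.1 lists shorter stay as an effect the dressing may have. Yet the only named source of resource use is silent for every inpatient day. If the instructions are followed literally, bed days, ward and theatre wound procedures and in-hospital dressings carry no cost.

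The gap is not random with respect to outcome. A day in hospital is a day without diary entries, so the observable cost window shrinks as stay lengthens. If SSI prolongs stay, participants with SSI lose more observable days than those without, and the numerator of the cost-utility ratio is affected differently in the two arms. Cost-effectiveness is a listed objective and secondary outcome, so this bears on a planned conclusion of the trial.

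There is also a practical side. A site told that no resource use is collected in hospital has no reason to record items the evaluation would later need.

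**Working it through.** **1. The protocol's own figures.** Section 1.1 gives at least 200,000 SSIs a year at £3500 each: 200,000 × £3500 = £700 million, as stated. Section 14.1 gives SSI rates of 25% and 15%, a 10-point difference. Its sample size also reproduces to within one participant per group (335 computed against 336 stated; 672/0.80 = 840) and is not in question.

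**2. Saving at stake.** Expected saving per participant = risk difference × cost per SSI = 0.10 × £3500 = £350.

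**3. Part not seen by a diary-only analysis.** The documents give no inpatient share f, so it is an assumption. Unobserved = f × £350.

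| Assumed f | Unobserved | Observed |
|---|---|---|
| 25% | £88 | £263 |
| 50% | £175 | £175 |
| 75% | £263 | £88 |
| 90% | £315 | £35 |

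**4. Observable days.** For a single index admission, diary days to day 30 = 30 − L, where L is length of stay. If the Day 30 review falls later in its window the diary runs on to it, but each inpatient day still removes one diary day.

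Illustration with assumed unit costs that are not in the documents: £10 per diary day and £200 per bed day.

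| L (days) | Diary days | Diary-only cost | Diary plus bed days |
|---|---|---|---|
| 5 | 25 | £250 | £1250 |
| 10 | 20 | £200 | £2200 |
| 14 | 16 | £160 | £2960 |
| 21 | 9 | £90 | £4290 |
| 30 | 0 | £0 | £6000 |

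With diary-day cost c and bed-day cost b, diary-only cost is c(30 − L), which falls with L. The combined cost is c(30 − L) + bL = 30c + (b − c)L, which rises with L whenever b exceeds c. The ordering by length of stay therefore reverses at any such pair, including £10/£400, £20/£400 and £50/£200. This compares stays of different length at a constant daily cost; it does not compare trial arms.

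**5. Does the SSI effect itself change sign?** Suppose SSI adds x inpatient days and raises the daily post-discharge cost from c0 to c1. To day 30, the diary-only cost of an SSI is c1(30 − L − x) − c0(30 − L). It is negative only if c1/c0 < (30 − L)/(30 − L − x). With L = 10 assumed:
- x = 2: 20/18 = 1.11
- x = 5: 20/15 = 1.33
- x = 10: 20/10 = 2.00

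So an SSI appears to save money only if daily cost after discharge rises by less than this factor. The documents give neither c1/c0 nor x. Continuing diaries after day 30 (section 9.3.7) add further cost on the SSI side.

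**The case against.** The strongest reply is that the sentence in 9.3.5 is a diary instruction. It sits under outpatient data capture, directly after the rule on crossing off inpatient days, and section 9.2 describes the diary as the route for patient-reported use. On that reading it says only that inpatients do not self-report. The inpatient data exist on other forms, section 15 already names NHS reference costs, nothing excludes those data from costing, and item-level costing is often left to a later plan.

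Much of this stands. A reader might infer that no inpatient data are collected, or that inpatient costs certainly enter at zero. The items listed in 8.1, 8.3, 8.4, 9.2, 9.3.6 and 10.3 rule out the former, and no section states the latter. A reader might also infer that long-stay participants will look cheapest and that the cost-effectiveness result will have the wrong sign. The documents do not support that either. The £350 calculation shows attenuation in the same direction. A reversal needs the CRF items to stay uncosted and post-discharge daily cost not to be much higher after SSI. A participant in hospital to day 30 with an unhealed SSI still contributes through the continuing diary. Section 1.1 lists inpatient and outpatient costs together without ranking them.

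What does not stand is that this is only silence left for a later plan. The protocol states a rule on the data source, and the rule conflicts with its stated perspective. The existing forms also have gaps. No section states that readmission length, ITU days, inpatient antibiotics or in-hospital changes of control dressings are recorded, although 8.1 expects most conventional dressings to be changed in hospital.

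**Conclusion.** The point holds as a conflict in the stated source of cost data. Followed as written, sections 9.2, 9.3.4, 9.3.5 and 15 leave inpatient cost out of an NHS-perspective evaluation, and observable days to day 30 fall one for one with length of stay. Incremental cost would be incomplete and probably biased.

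Of an expected £350 saving per participant, about £88-£315 would go unobserved. This rests on the protocol's £3500, which is an average over UK SSIs generally and not specific to emergency laparotomy; on the target 10-point reduction being achieved; and on an assumed inpatient share of 25-90%. The net direction of bias cannot be settled from the documents.

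The matter is confined to a secondary outcome. The primary SSI comparison and the sample size are unaffected. It should be corrected because the conflict is explicit and most of the data needed are already recorded.

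**What to change.** Amend sections 9.2, 9.3.5 and 15 together.

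- State that the base-case cost combines the diary for time out of hospital, including continuing diaries after day 30, with inpatient items already recorded: index length of stay, wound-related readmissions, Return to Theatre forms, wound interventions on the Day 7 and Day 30 CRFs, and in-hospital SUNPD use. Cost them from the national sources section 15 already names.
- Limit the 9.3.5 sentence to participant self-report in the diary, so that sites do not read it as a bar on recording inpatient resource use.
- Check whether the CRFs hold readmission length and ITU days, and add fields if not. Clavien-Dindo grade IV indicates an ITU admission for a wound complication but gives no duration.

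The cost is revised wording, some extra costing work and possibly a few CRF fields. Making the change early matters mainly for those fields, since length of stay and the existing forms can be costed at any time. No change to the randomised comparison or clinical procedures is needed.

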9.3.6. Day 30 assessment

At day 30 (assessment window: Days 30-44; with day 0 being the day of randomisation), a blinded review will take place. If an in-person wound assessment is not possible as the patient is not able to return for an outpatient or research visit to the hospital, this wound assessment is to be conducted using real-time remote video consultation. Telephone follow up assessments of the patient and their wound status can be used as a last resort. The wound will be assessed for an infection according to the CDC SSI criteria. As part of the assessment the highest Clavien-Dindo grade of wound complication that occurred since surgery will be recorded²⁶.

As part of this wound inspection, the Wound Assessment Day 30 CRF will be completed, which includes asking the participant to rate their wound pain using a 10-point visual analogue scale. The participant will also be asked to complete the Quality of Life questionnaires, EQ-5D-5L and SF-12, if they have not already done so in the Patient Diary. If no wound infection is evident then the participant will have completed the study.

Prior to undergoing the Day 30 review, the participant will have completed the Bluebelle wound healing questionnaire in the Patient Diary. This assessment will be repeated with the wound assessor as part of the Day 30 review and will allow SUNRISE to compare results with the Bluebelle questionnaire. However, if the participant remains an inpatient at the time of the Day 30 assessment, the questionnaire does not need to be completed by the patient or repeated with the wound assessor.

In order to encourage and facilitate patients to attend their in-person wound review at day 30 (where appropriate), their travel expenses in the form of taxi fares, public transport costs or parking charges will be supported.

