9. OUTCOME MEASURES AND STUDY PROCEDURES

9.1. Primary Outcome

The primary outcome is SSI within 30 days of surgery, as defined by the internationally accredited CDC criteria. Wound assessment will be conducted at day 7 post-operation or on discharge (whichever is sooner). It will also be performed at day 30 post-operation, by a blinded and trained wound assessor. The intervening period will be covered by a structured patient diary.

The following CDC definition will be used to identify an SSI:

- The infection must occur within 30-days of the index operation

AND

- The patient must have at least one of the following:
 - Purulent drainage from the wound
 - Organisms are detected from a wound swab
 - Wound opened spontaneously or by a clinician AND, at the surgical wound, the patient has at least one of: pain or tenderness; localised swelling; redness; heat; systemic fever ($>38^{\circ}\text{C}$).
 - Diagnosis of SSI by a clinician or on imaging

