9.4. Schedule of Assessments

Activity/CRF		Pre-theatre	In-theatre	Day 7 post-op (-2/+3 days)	Day 14 post-op (± 2 days)	Day 21 post-op (± 2 days)	Day 30 post-op (+ 14 days)	Day 30+
Patient identification and screening		On-call surgical team						
Patient consent	• Standard	Patient & Member of the research team						
	• Delayed (UK only)	Consultee/Representative & Member of the research team		Patient & Member of the research team when capacity regained				
Randomisation form		Started pre-theatre by the research team	Surgeon or member of the research team					
In-Theatre form			Ideally an operating surgeon, or member of the research team					
Wound Assessment Day 7 or on Discharge (if sooner)^{1,2}				Member of the research team				
EQ-5D-5L		Completed by the participant		Completed by the participant	Completed by the participant	Completed by the participant	Completed by the participant	
SF-12		Completed by the participant		Completed by the participant			Completed by the participant	
Patient diary				Completed daily by the participant following discharge from hospital until they undergo the Day 30 wound review				Patients to continue with a diary if they have an ongoing SSI
Bluebelle wound healing questionnaire							Completed by the participant independently, and then by the participant with a blinded member of the research team reviewing wound	
Wound Assessment Day 30¹							Completed by a blinded member of the research team as an in-person or remote (video) review	
SAE reporting			All serious adverse events by member of the research team using SAE form or wound assessment CRF if excluded from expedited reporting					Related serious adverse events only
Return to theatre form			Member of the research team for any return to theatre following patient returning to theatre					
PI Declaration form for CFR data								Completed by PI at the end of each participant's involvement

¹ Assessment of pain undertaken by a member of the research team by asking the participant and recording the response on the CRF

² Score of patient acceptability of dressing undertaken by a member of the research team by asking the participant and recording the response on the CRF

Table 1: Table of assessments. Member of the research team is a person named on the local delegation log and given the assigned duty.

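### The wound-complication outcome is limited to 30 days, but its grade is collected from surgery up to a review that may fall as late as day 44, with no cut at day 30

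*Protocol*

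**What the plan says.** Section 9.2 of the protocol defines the secondary outcome as "Wound complications within 30 days post-surgery as graded by Clavien-Dindo scale".

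Section 9.3.6 describes how it is collected: "At day 30 (assessment window: Days 30-44; with day 0 being the day of randomisation), a blinded review will take place". At that review, the assessor is to record "the highest Clavien-Dindo grade of wound complication that occurred since surgery". Section 1.2.2 and the schedule in section 9.4 give the same window of 30 to 44 days. Randomisation takes place in theatre during skin closure, so counting from randomisation is in practice counting from the operation.

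For the primary outcome, section 9.1 sets a time condition: "The infection must occur within 30-days of the index operation". Section 9.3.6 then says of the review: "The wound will be assessed for an infection according to the CDC SSI criteria". It gives no rule for dating the onset of an infection first seen at a review after day 30.

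The patient diary also runs to the review and not to day 30. Section 9.4 has it "Completed daily by the participant following discharge from hospital until they undergo the Day 30 wound review".

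**The concern.** The definition and the collection instruction cover different periods. An assessor who follows section 9.3.6 to the letter at a day 40 visit will include whatever happened on days 31 to 40, and nothing in the protocol tells the assessor to leave it out. The outcome reported as a 30-day one would then cover 30 days for some participants and up to 44 for others, depending on when the visit could be arranged.

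The form of the data makes this hard to repair at analysis. The protocol describes one maximum grade and mentions no date for it, and an undated maximum cannot be cut back to day 30. Dating the maximum alone would not be enough either: if the worst grade was reached on day 38, the worst grade up to day 30 is lost.

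What is at stake is a secondary outcome that does not match its definition. Late events occur well after the SUNPD has come off (day 7 at the latest), so they are more likely to dilute a difference than to add to it.

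**Working it through.** **The two periods side by side**

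- Defined period (section 9.2): 30 days.
- Collected period (section 9.3.6): surgery to the review, so 30 to 44 days.
- Largest excess: 44 − 30 = 14 days, and 44/30 = 1.47 times the defined period. This is the maximum, for a review on day 44. A participant reviewed on day 30 has no excess.

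**What the instruction does to identical courses**

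| Course | Review on day 30 | Review on day 44 | Outcome as defined |
|---|---|---|---|
| Free of complications to day 30, antibiotics for the wound on day 38 (grade II in Appendix 2) | none | II | none |
| Grade I on day 20, surgical intervention on day 38 (grade III) | I | III | I |

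The first course changes the yes/no outcome to which section 14.2.2 applies a log-binomial model. The second changes only the reported grade.

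**Size, under an assumption**

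The protocol gives neither a rate of wound complications nor a rate of late events. As an illustration only, I borrow the SSI design rates in section 14.1: control p₁ = 0.25, SUNPD p₂ = 0.15, two-sided 5%, 90% power.

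The plan's own figure comes first. With p̄ = 0.20,

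n = [1.960·√(2·0.20·0.80) + 1.2816·√(0.25·0.75 + 0.15·0.85)]² / 0.10² = (1.1087 + 0.7193)² / 0.01 ≈ 334.2, so 335 per group.

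The protocol states 336, which agrees within rounding, and 672/0.80 = 840. The sample size is not in dispute.

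Now let e be the proportion of participants free of the event at day 30 who have a late event counted, equal in both arms. Then p′ = p + (1 − p)·e. The extra participants counted among 672 are 336·e·(0.75 + 0.85).

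| e (assumed) | Control | SUNPD | Relative risk | Extra counted of 672 | Power at 336 per group |
|---|---|---|---|---|---|
| 0 | 0.2500 | 0.1500 | 0.60 | 0 | 90.2% |
| 1% | 0.2575 | 0.1585 | 0.62 | 5 | 88.7% |
| 2% | 0.2650 | 0.1670 | 0.63 | 11 | 87.2% |
| 3% | 0.2725 | 0.1755 | 0.64 | 16 | 85.6% |
| 5% | 0.2875 | 0.1925 | 0.67 | 27 | 82.4% |

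The value of e depends on how late reviews actually fall: if most take place on day 30 or soon after, it is close to 0. The power column shows the direction of the effect for an outcome with these rates. The trial is not powered on wound complications.

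**The primary outcome**

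Section 9.1 joins the 30-day condition to the clinical criteria, so an infection that begins on day 36 is not an SSI for this trial. That holds whenever the review takes place. What section 9.3.6 leaves open is how the assessor establishes that an infection first seen on, say, day 40 began by day 30.

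**The case against.** The strongest reply is that section 9.2 governs and section 9.3.6 is only a collection instruction. Grades in Appendix 2 follow largely from management (ward procedure, antibiotics, surgery or radiology, intensive care), and much of that leaves dated traces. The diary is completed daily after discharge and covers interventions, diagnosis of wound infection and antibiotics (section 9.3.5). It is checked with the participant at the review (section 11.3). Section 8.4 requires a form for any return to theatre within 30 days. The Day 30 CRF is not shown and may carry dates, and derivation rules may sit in the SAP.

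Part of this stands: onset can often be reconstructed, and a daily diary that runs past day 30 can simply be cut there. But inpatients do not complete the daily questions (section 9.3.4), and after a remote review the diary is posted back (section 9.3.5), so the assessor may not have it to hand when grading. None of these sources changes what the assessor is told to record. Even if the CRF does carry dates, the wording of section 9.3.6 still conflicts with section 9.2.

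Three stronger readings are tempting, and the protocol does not support them:

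- A reader might infer that SSIs from days 31 to 44 count towards the primary outcome. Section 9.1 excludes them by definition. Wound-related readmission is likewise limited to 30 days in section 9.2.
- A reader might infer a bias between arms. The window is the same in both arms, the Day 30 assessor is blinded (section 7.5), and nothing in the protocol suggests that review timing differs by allocation. Bias would need that further condition.
- A reader might see the one-sided window as the fault. It is sensible, because a visit before day 30 would leave the outcome period incompletely observed.

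**Conclusion.** The point holds for the Clavien-Dindo wound-complication outcome. Sections 9.2 and 9.3.6 define different periods, and following section 9.3.6 as written yields an outcome that can run up to 14 days past its stated limit, by an amount that varies between participants.

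The expected consequence is unequal observation time and some dilution. The size is unknown. If 1% to 5% of participants event-free at day 30 had a late event counted in each arm, a relative risk of 0.60 would move to between 0.62 and 0.67. Both the late-event rate and the use of SSI rates for this outcome are assumptions.

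For the primary outcome the remaining gap is one of procedure: how onset is dated when an infection is first seen after day 30. The sample size of 840 is unaffected. The change is worth making because it is cheap and brings the recorded outcome into line with its definition.

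**What to change.** 1. In section 9.3.6, replace 'since surgery' with 'up to and including day 30 after the index operation' in the sentence on the Clavien-Dindo grade. This has to be in the instruction itself, since a date on the overall maximum would not recover the worst grade by day 30.
2. On the Day 30 CRF, for any SSI or wound complication found at a review after day 30, record the onset date, or 'onset on or before day 30: yes/no', using the diary and hospital records. If the CRF already has such a field, refer to it in section 9.3.6.
3. Keep the window of days 30 to 44, and list events with later onset separately.

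The cost is one phrase in the protocol and one field on an existing form. The drawback is that some onset dates will be approximate, above all where the diary is incomplete or the participant was still in hospital.
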